### 5.3.4. Contraception

The investigator or his or her designee, in consultation with the male participant, will confirm that the participant has selected an appropriate method of contraception for the individual male participant and his partner(s) from the permitted list of contraception methods (see [Appendix 4](#)) and will confirm that the participant has been instructed in its consistent and correct use. At time points indicated in the [SoA](#), the investigator or designee will inform the male participant of the need to use effective contraception consistently and correctly and document the conversation and the male participant's affirmation in the participant's chart (participants need to affirm their consistent and correct use of at least 1 of the selected methods of contraception). In addition, the investigator or designee will instruct the participant to call immediately if the selected contraception method is discontinued or if pregnancy is known or suspected in the participant's female partner.

Female participants will not require use of contraception as they cannot be women of childbearing potential.

## 5.4. Screen Failures

Screen failures are defined as participants who consent to participate in the clinical study but are not subsequently randomly assigned to study intervention/enrolled in the study. A minimal set of screen failure information is required to ensure transparent reporting of screen failure participants to meet the CONSORT publishing requirements and to respond to queries from regulatory authorities. Minimal information includes demography, screen failure details, eligibility criteria, and any SAE.

Individuals who do not meet the eligibility criteria for participation in this study (screen failure) may not be rescreened. As an exception, a participant who otherwise qualified for this study but did not enroll due to positive COVID-19 test, due to recent vaccination (see [Section 5.2](#)), or due to exhibiting COVID-19-related symptoms or potential exposure, may be rescreened after an appropriate interval, if judged appropriate by the investigator. In such cases, all screening procedures must be repeated and the participant assigned a new 8-digit SSID.

A participant who qualified for this study but did not enroll for administrative reasons (eg, delays in IP shipping, cohort filled) may be re-screened. In such cases, all screening procedures must be repeated (if the time between screening and dosing exceeds 28 days) and the participant assigned a new 8-digit SSID.

## 6. STUDY INTERVENTION(S) AND CONCOMITANT THERAPY

Study intervention is defined as any investigational intervention(s), marketed product(s), placebo, medical device(s), or study procedure(s) intended to be administered to a study participant according to the study protocol.

For the purposes of this protocol, the term investigational product may be used synonymously with study intervention.

For the purposes of this protocol, study intervention refers to PF-07081532 or matching placebo.

### 6.1. Study Intervention(s) Administered

PF-07081532 and matching placebo will be supplied by Pfizer as tablets. The tablets will be supplied to the CRU in bulk along with individual dosing containers for unit dosing.

#### 6.1.1. Administration

On Day 1, participants will receive IP at approximately 0800 hours (plus or minus 2 hours). Dosing of IP is planned to occur in the fed state, ie, with breakfast. Details on meals and dietary requirements and activity restrictions are given in [Lifestyle Considerations](#) section of the protocol. Investigator site personnel will administer investigational product with approximately 240 mL ambient temperature water. Participants will swallow the investigational product whole, and will not manipulate or chew the investigational product prior to swallowing.

- Blinding will be maintained by keeping the number of tablets the same for PF-07081532 and placebo within a given cohort.

## **6.2. Preparation, Handling, Storage, and Accountability**

1. The investigator or designee must confirm appropriate temperature conditions have been maintained during transit for all study interventions received and any discrepancies are reported and resolved before use of the study intervention.
2. Only participants enrolled in the study may receive study intervention and only authorized site staff may supply or administer study intervention. All study interventions must be stored in a secure, environmentally controlled, and monitored (manual or automated recording) area in accordance with the labeled storage conditions with access limited to the investigator and authorized site staff. At a minimum, daily minimum and maximum temperatures for all site storage locations must be documented and available upon request. Data for nonworking days must indicate the minimum and maximum temperatures since previously documented for all site storage locations upon return to business.
3. Any excursions from the study intervention label storage conditions should be reported to Pfizer upon discovery along with any actions taken. The site should actively pursue options for returning the study intervention to the storage conditions described in the labeling, as soon as possible. Once an excursion is identified, the study intervention must be quarantined and not used until Pfizer provides permission to use the study intervention. Specific details regarding the definition of an excursion and information the site should report for each excursion will be provided to the site in the IP manual.
4. Any storage conditions stated in the SRSD will be superseded by the storage conditions stated on the label.
5. Study interventions should be stored in their original containers.
6. See the IP manual for storage conditions of the study intervention.
7. The investigator, institution, or the head of the medical institution (where applicable) is responsible for study intervention accountability, reconciliation, and record maintenance (ie, receipt, reconciliation, and final disposition records), such as the IPAL or sponsor-approved equivalent. All study interventions will be accounted for using a study intervention accountability form/record.
8. Further guidance and information for the final disposition of unused study interventions are provided in the IP manual. All destruction must be adequately documented. If destruction is authorized to take place at the investigator site, the investigator must ensure that the materials are destroyed in compliance with applicable environmental regulations, institutional policy, and any special instructions provided by Pfizer.

Upon identification of a product complaint, notify the sponsor within 1 business day of discovery as described in the IP manual.

### **6.2.1. Preparation and Dispensing**

Study intervention and placebo will be prepared by qualified unblinded site personnel according to the IP manual. The study intervention will be administered in a blinded fashion to the participants.

## **6.3. Measures to Minimize Bias: Randomization and Blinding**

### **6.3.1. Allocation to Study Intervention**

All participants will be assigned to randomized study intervention using a randomization scheme, maintained by Pfizer (or designated CRO vendor). Investigators will remain blinded to each participant's assigned study intervention throughout the course of the study. Unblinded personnel will access randomization scheme to prepare or dispense the appropriate study treatment.

The randomization scheme/list will be provided directly and securely to the site pharmacist(s). The unblinded pharmacist(s) will be responsible for the preparation and dispensing of all study intervention and will endeavor to ensure that there are no differences in time taken to dispense or visual presentation following randomization and no blinded site staff are able to view the administration.

In the event of a Quality Assurance audit, the auditor(s) will be allowed access to unblinded study intervention records at the site(s) to verify that randomization/dispensing has been done accurately.

### **6.3.2. Breaking the Blind**

The method for breaking the blind in this study will be manual. A sealed envelope that contains the study intervention assignment(s) for each participant will be provided to the investigator. The sealed envelope will be retained by the investigator (or representative) in a secured area. In case of an emergency, the investigator has the sole responsibility for determining if unblinding of a participant's treatment assignment is warranted. Participant safety must always be the first consideration in making such a determination. If the investigator decides that unblinding is warranted, the investigator should make every effort to contact the sponsor prior to unblinding a participant's treatment assignment unless this could delay further management of the participant. If a participant's treatment assignment is unblinded, the sponsor must be notified within 24 hours after breaking the blind. When the blinding code is broken, the reason must be fully documented and entered on the CRF/DCT.

Once the study is complete, all envelopes (sealed and opened) must be inventoried and retained until authorization for destruction has been provided.

#### 6.4. Study Intervention Compliance

Participants will receive study intervention directly from the investigator or designee, under medical supervision. The date and time of each dose administered in the clinic will be recorded in the source documents and recorded in the CRF. The dose of study intervention and study participant identification will be confirmed at the time of dosing by a member of the study site staff other than the person administering the study intervention. Study site personnel will examine each participant's mouth to ensure that the study intervention was ingested.

#### 6.5. Dose Modification

Refer to [Section 4.3](#) for details of dosing scheme, and circumstances under which modifications may be acceptable.

#### 6.6. Continued Access to Study Intervention After the End of the Study

No intervention will be provided to study participants at the end of their study participation.

#### 6.7. Treatment of Overdose

For this study, any dose of PF-07081532 greater than 2.5 g is projected to result in exposures greater than 404255 ng/mL for  $C_{max}$  (ie, 152 ng/mL unbound) or 5664894 ng·h/mL for  $AUC_{24}$  (ie, 2130 ng·h/mL unbound) within a 24-hour time period and will be considered an overdose. The exposures above are based on the unbound exposures at the NOAEL in the NHP toxicity study (see [Section 2.2.1.3](#)) after accounting for protein binding in humans.

There is no specific treatment for an overdose.

In the event of an overdose, the investigator/treating physician should:

1. Contact the medical monitor within 24 hours.
2. Closely monitor the participant for any AEs/SAEs and laboratory abnormalities for at least 5 half-lives or 28 calendar days after the overdose of PF-07081532 (whichever is longer).
3. Document the quantity of the excess dose as well as the duration of the overdose in the CRF.
4. Overdose is reportable to Pfizer Safety **only when associated with an SAE**.
5. Obtain a blood sample for PK analysis within 3 days from the date of the last dose of study intervention if requested by the medical monitor (determined on a case-by-case basis).

Decisions regarding dose interruptions or modifications will be made by the investigator in consultation with the medical monitor based on the clinical evaluation of the participant.

## **6.8. Concomitant Therapy**

### **6.8.1. Permitted Medications**

Participants may be on certain concomitant medications that have been prescribed to treat concurrent diseases such as hyperlipidemia and hypertension. Attempts must be made not to alter the doses and regimens of the background/concomitant medications after randomization and for the duration of participation in this study. Any changes must be captured in the CRF. Where applicable, participants are expected to bring their supply of permitted prescription medications prior to confinement to the unit.

Medications, prescription or non-prescription, or herbal supplements not specifically listed in the protocol may be permitted, but only after review and approval by the sponsor

#### **6.8.1.1. Metformin**

All participants enrolling with T2DM are required to be taking metformin monotherapy at a minimum dose of 500 mg/day. On all study days while in the CRU, participants will be given their morning dose of metformin at the same time as PF-07081532/placebo.

Sponsor will not provide metformin during the study and participants are expected to bring their current supply of metformin prior to confinement to the unit.

For participants taking metformin more frequently than once a day, the investigator will determine the appropriate times during the day to administer those doses. For metformin (required) and other permitted concomitant medications, the timing of administration should be the same between inpatient days, and care should be taken to minimize changes to the participants stable medication routine. The dose of metformin, where possible, is expected to remain the same until completion of study participation ie, last follow-up visit.

#### **6.8.1.2. Antihypertensive and Lipid-Modifying Agents**

The use of background antihypertensive and/or lipid-modifying agent(s) is permitted, unless prohibited as per Prohibited Medications section of the protocol. Doses of such agents must be stable for at least 4 weeks prior to screening and are expected to remain the same until completion of study participation (ie, follow-up visit).

#### **6.8.1.3. Medications for Management of Nausea and Vomiting**

Nausea and vomiting have been reported with administration of GLP-1R agonists. Participants experiencing such symptoms may be managed conservatively with bed rest and/or fluid management at the discretion of the investigator. If the nausea and vomiting are not amenable to conservative management, anti-emetics (eg, prochlorperazine, promethazine, ondansetron) may be administered at the investigator's discretion with notification to the sponsor and entry in the CRF.

### **6.8.2. Prohibited Medications**

Use of medications, other than metformin, for glycemic control is not permitted in this study.

### **6.8.2.1. Medications Not Permitted During the Study due to Potential Drug-Drug Interaction and Other Prohibited, Prior and Concomitant Medications**

See [Appendix 8](#) for list of prohibited concomitant medications due to potential drug-drug interaction and [Appendix 9](#) for a list of other, prohibited prior and concomitant medications.

Sites are encouraged to contact the sponsor should there be questions as to whether a medication is permitted or prohibited.

### **6.8.3. Rescue Medicine**

There is no rescue therapy to reverse AEs observed with PF-07081532; standard medical supportive care must be provided to manage any AEs (see [Section 6.8.1.3](#)).

For medical management of hypoglycemia, the investigator may administer oral carbohydrate, glucagon, or IV glucose according to his or her medical judgment. At a minimum however, treatment or administration of a scheduled meal should be given if glucose falls <60 mg/dL for at least 15 minutes, irrespective of whether the participant exhibits symptoms. Investigators may choose to administer treatment sooner if participants have bothersome symptoms of hypoglycemia along with glucose values of  $\leq 70$  mg/dL.

No rescue therapy will be provided for hyperglycemia. If a participant has sustained elevated fasting plasma glucose concentrations that are >270 mg/dL on 3 consecutive measurements over 3 days, that participant will be discontinued, and the investigator will recommend further appropriate glycemetic treatment according to the local healthcare standards and national guidelines.

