**Table 2. Detailed Schedule (selected study days)**

	Study Day	Hours Relative to Dosing at 0H a													
		0	0.25	0.5	1	1.5	2	3	4	6	8	10	12	16	24 b
Triplicate, supine 12-lead ECG	Days -1, 1, and 42	x			x		x		x		x		x		x
Triplicate, supine vital sign (blood pressure and pulse)	Days -1, 1, and 42	x			x		x		x		x		x		x
Fasting fingerstick blood glucose measurement b,c	All inpatient days	x													
Liquid meal (for MMTT) d	Days -1, 28 e and 42	x													
Standardized meal/snack f	all inpatient days	x g							x			x		x	
Blinded investigational product administration	Daily: Day 1 to Day 42	x h													
Blood sampling for:															
- Safety laboratory tests i	Days -1, 28, and 42	x j													
- HbA1c k , TSH	Days -1, 28, and 42	x j													
- Plasma glucose l	Days -1, 28 e and 42	x j	x	x	x	x	x	x	x	x	x	x	x	x	x
- Plasma insulin l	Days -1 and 42	x j, m	x	x	x	x	x	x	x						
- Plasma C-peptide k , glucagon k )	Days -1 and 42	x j	x	x	x	x	x	x	x						
- Free T4, calcitonin, amylase, lipase, lipids	Days -1, 28, and 42	x j													
- PF-07081532 PK	Days 1 and 42	x		x	x		x		x	x	x	x	x	x	x
- 4-β-hydroxycholesterol/cholesterol	Days 1 and 42	x													
- Retained research samples for Prep D1.5	Day -1 only n	x													
- Retained research samples for Prep B1.5 and Prep B2.5	Day -1 and Day 42	x													
Urine sampling for:															
- Urinalysis and microscopy, as appropriate	Days -1, 28, and 42	x													

- On Day -1, time of 0H procedures to match approximate planned clock time of collection on Day 1. All other days, 0H procedures to be completed pre-dose.
- The 24H sample is to be collected prior to dosing on the following morning, as indicated in [Table 1](#).
- Fingerstick glucose via glucometer on admission to CRU and prior to breakfast on all inpatient days; may be more frequent at the discretion of the investigator.
- Liquid meal given at 0H (or on Day -1 at the anticipated clock time of Day 1 dose) to be consumed over 10 mins. The 0.25 H sample is 5 minutes after completion of the liquid meal. This procedure is to be conducted in participants enrolling with T2DM only.

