- Indicated procedures will be conducted on Days -1, 28, and 42 for Cohort 1; decision for Day 28 procedures in subsequent cohorts will be provided in writing prior to initiation of dosing for each cohort.
- Standardized meals/snacks to be provided on all days while inpatient; identical meals/snacks on days when MMTT is being conducted. Refer to [Section 5.3](#).
- Standard breakfast NOT provided on days when MMTT is being conducted; refer to [Section 5.3](#).
- Dosing to occur with breakfast or liquid meal daily from Day 1 to day 42, inclusive.
- See [Appendix 2: Clinical Laboratory Tests](#) for safety lab tests to be collected at each timepoint.
- See [Section 5.3](#) for fasting requirements.
- Participants enrolling with T2DM only.
- Fasting (0H) sample is to be collected in all participants. Post-dose timepoints in participants enrolling with T2DM only.
- Fasting (time 0H only) insulin to be measured in triplicate on Day -1 and Day 42, all other measurements single, see [Section 8.9.2](#).
- If not collected on the designated collection day, collect at the next available time point when biospecimens are being collected in conjunction with a participant visit.

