### **Diagnostic Assessments:**

14. A positive urine drug screen at screening or admission.

**Note:** Participants who have been medically prescribed benzodiazepines and report the use of these drugs to the investigator at the screening visit may be allowed to participate if approved by the sponsor.

15. Positive testing at screening for HIV, HBsAg, HBcAb, HBsAb or HCVAb. Positive COVID-19 test at screening or admission.

**Note:** A positive HBsAb due to hepatitis B vaccination is permissible.

16. Screening supine BP  $\geq 160$  mm Hg (systolic) or  $\geq 100$  mm Hg (diastolic) following at least 5 minutes of supine rest.

If BP is  $\geq 160$  mm Hg (systolic) or  $\geq 100$  mm Hg (diastolic), the BP should be repeated 2 more times and the average of the 3 BP values should be used to determine the participant's eligibility.

17. Screening 12-lead ECG that demonstrates clinically relevant abnormalities that may affect participant safety or interpretation of study results (eg, baseline QTcF interval  $>450$  msec, complete LBBB, signs of an acute or indeterminate-age myocardial infarction, ST-T interval changes suggestive of myocardial ischemia, second- or third-degree AV block, or serious bradyarrhythmias or tachyarrhythmias).

If QTcF exceeds 450 msec, or QRS exceeds 120 msec, the ECG should be repeated 2 more times and the average of the 3 QTcF or QRS values should be used to determine the participant's eligibility. Computer-interpreted ECGs should be overread by a physician experienced in reading ECGs before excluding participants.

18. Participants with **ANY** of the following abnormalities in clinical laboratory tests at screening, as assessed by the study-specific laboratory and confirmed by a single repeat test if deemed necessary:

- AST or ALT level  $\geq 1.5$  times ULN;

- Total bilirubin level  $\geq 1.5$  times the ULN; participants with a history of Gilbert's syndrome may have direct bilirubin measured and would be eligible for this study provided the direct bilirubin level is  $\leq$  ULN;
- TSH > ULN;
- Fasting C-peptide <0.8 ng/mL;
- Serum calcitonin > ULN;
- Amylase > ULN;
- Lipase > ULN;
- eGFR <60 mL/min/1.73m^2 as calculated by MDRD equation;
- FPG >270 mg/dL at **screening or admission**.

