### 7.1.3. Laboratory Abnormalities

All of the following laboratory abnormalities require discontinuation if they are confirmed:

- Hyperglycemia: see [Section 6.8.3](#) and [Section 8.2.4.2](#);
- Creatine kinase >10 × ULN;

Note: Urine myoglobin and SCr will be performed as reflex testing for any participant with creatine kinase >10 × ULN.

- AST or ALT that meets ANY of the following:
  - >3 × ULN with at least one total bilirubin value >2 × ULN;
  - >3 × ULN accompanied by signs or symptoms consistent with hepatic injury (eg, new onset elevated PT/INR);
  - Two sequential AST or ALT elevations >5 × ULN, regardless of total bilirubin or accompanying signs or symptoms.

NOTE: See also [Appendix 6](#) for potential cases of drug-induced liver injury.

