**Table 6. Protocol-Required Safety Laboratory Assessments**

Hematology	Chemistry/Other	Urinalysis	At specified times
Hemoglobin Hematocrit RBC count MCV MCH MCHC Platelet count WBC count Total neutrophils (Abs) Eosinophils (Abs) Monocytes (Abs) Basophils (Abs) Lymphocytes (Abs)	BUN/Urea Serum Creatinine a Plasma Glucose (fasting) Calcium Sodium Potassium Chloride Total CO 2 (bicarbonate) AST ALT Total bilirubin Direct bilirubin Indirect bilirubin Alkaline phosphatase Uric acid Albumin Total Bile Acids	pH Glucose (qual) Protein (qual) Blood (qual) Ketones Nitrites Leukocyte esterase Urobilinogen Urine bilirubin Microscopy b	At screening only: 
 
• FSHc
 
• HBsAg
 
• HCVAb
 
• HBcAb
 
• HBsAb
 
• HIV
 
• C-peptided
 
 At times specified in the SoA: 
 
• Urine drug screeninge
 
• Free T4
 
• TSH
 
• Calcitonin
 
• Amylase
 
• Lipase
 
• Lipid profile (ie, total cholesterol, triglycerides, direct HDL, direct LDL)
 

- GFR will be calculated using the MDRD equation:  $GFR (ml/min/1.73m^2) = 175 \times \text{standardized Serum Creatinine} - 1.154 \times \text{age} - 0.203 \times 1.212 [\text{if Black}] \times 0.742 [\text{if female}]$ .
- Only if urine dipstick is positive for blood, protein, nitrites, or leukocyte esterase.
- For confirmation of postmenopausal status in female participants only.
- C-peptide is collected as part of safety laboratory tests at Screening (collected as part of MMTT at other times indicated in [Table 1](#) and [Table 2](#)).
- The minimum requirement for drug screening includes cocaine, THC, opiates/opioids, benzodiazepines, and amphetamines (others are site and study specific).

The investigator must review the laboratory report, document this review, and record any clinically relevant changes occurring during the study in the AE section of the CRF.

Safety/laboratory/analyte results obtained following first dose of the study intervention (Day 1) that could unblind the study (ie, glucose, insulin, glucagon, C-peptide, HbA1c, and PK),

will not be reported to investigative sites or other blinded personnel until the study has been unblinded.

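### The hyperglycaemia stop needs three consecutive days of fasting plasma glucose, but the schedule gives at most two and the site does not see the results; the daily fingerstick is not named as the trigger

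*Protocol*

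**What the plan says.** Protocol Section 6.8.3 (Rescue Medicine) offers no rescue for hyperglycaemia. Instead, it sets this rule for anyone with "sustained elevated fasting plasma glucose concentrations that are >270 mg/dL on 3 consecutive measurements over 3 days, that participant will be discontinued". Further treatment is then a matter for the investigator to recommend. Section 7.1.3 makes this binding: "All of the following laboratory abnormalities require discontinuation if they are confirmed". Its hyperglycaemia entry refers to Sections 6.8.3 and 8.2.4.2.

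Fasting plasma glucose appears elsewhere as a laboratory measure. Exclusion criterion 18, whose tests are assessed by the study-specific laboratory, includes "FPG >270 mg/dL at screening or admission". Table 6 in Appendix 2 lists fasting plasma glucose in the chemistry panel. Section 8.2.4.1 separates the fingerstick, which stays in source documents, from the laboratory glucose that enters the database.

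Table 2 schedules plasma glucose profiles on Days -1, 28 and 42. On timing, "The 24H sample is to be collected prior to dosing on the following morning". For the Day 28 profile after Cohort 1, the "decision for Day 28 procedures in subsequent cohorts will be provided in writing prior to initiation of dosing for each cohort".

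Section 8 and Appendix 2 both withhold glucose results obtained after the first dose from sites and other blinded personnel until unblinding. Neither gives a safety exception. The fasting fingerstick is taken and read at the site every inpatient morning (Section 8.2.4.1).

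**The concern.** A mandatory safety stop should say which measurement triggers it, and that measurement should reach whoever has to act. Here the named analyte is not scheduled often enough to complete the rule, and its results do not go to the site. The measurement that is frequent enough and visible to the site, the daily fingerstick, is not linked to the rule. Section 8.2.4.1 gives the fingerstick one action threshold, below 70 mg/dL, with a repeat reading, a venous sample and adverse event recording. It has no high-side counterpart. A reader who follows Section 7.1.3 to Section 8.2.4.2 finds only definitions of hypoglycaemia.

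At stake is consistent use of the written protection against sustained hyperglycaemia in participants with HbA1c up to 10.5% who may take no glucose-lowering drug except metformin. Sites or cohorts could differ on whether a fingerstick counts, whether it needs confirmation, and who declares the rule met. No bias in any analysis is claimed.

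**Working it through.** The plan gives no figure to reproduce. The check counts how many consecutive mornings of scheduled laboratory fasting glucose the rule could draw on.

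**Inputs**
- Rule: 3 consecutive measurements over 3 days (Section 6.8.3), taken as 3 consecutive fasting mornings.
- Mornings after the first dose and up to the last dose: Days 2 to 42, which is 41 mornings.
- Laboratory mornings from Table 2: Day 28, Day 29 (the 24H sample of the Day 28 profile) and Day 42. The Day 28 safety laboratory sample remains in later cohorts even if the profile is dropped.
- Laboratory mornings from Table 1: Days 8 and 14. The columns of Table 1 are not reliably aligned in the text available, so these two days are an assumption, and results are shown with and without them.
- Fingerstick: every inpatient morning.

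**Formulas**
- Three-morning windows = 41 - 3 + 1 = 39.
- Unscheduled samples needed in a window = 3 minus the laboratory mornings in that window.

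**Cohort 1, by first day of the window (2 to 40)**
- Day 8 lies in windows starting on Days 6, 7 and 8; Day 14 in those starting on 12, 13 and 14; Day 42 only in the one starting on 40.
- Days 28 and 29 lie in windows starting on 26 to 29. Those starting on 27 and 28 contain both days; those starting on 26 and 29 contain one.
- Two laboratory mornings: 2 windows. One: 3 + 3 + 2 + 1 = 9. None: 39 - 11 = 28.

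| Schedule | Laboratory mornings | Longest run | Windows needing 1 / 2 / 3 unscheduled samples |
|---|---|---|---|
| Cohort 1 | 8, 14, 28, 29, 42 | 2 | 2 / 9 / 28 |
| Cohort 1, without Days 8 and 14 | 28, 29, 42 | 2 | 2 / 3 / 34 |
| Later cohort, no Day 28 profile | 8, 14, 28, 42 | 1 | 0 / 10 / 29 |
| Same, without Days 8 and 14 | 28, 42 | 1 | 0 / 4 / 35 |

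No window contains 3 scheduled laboratory mornings under any of these schedules. Adding possible safety laboratory samples on Days 22 and 36 leaves the longest run at 2. So does counting Day 43, which follows the last dose. The daily fingerstick supplies 3 of 3 mornings in all 39 windows.

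These counts show only that the schedule cannot complete the rule. They do not measure harm or how often the rule would be met; the documents do not give that frequency and none is assumed.

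**The case against.** A reader might infer that the stop can never fire, or that it contradicts the withholding rule. The documents do not support either. Withholding covers sites and other blinded personnel only. The trial is sponsor-open, and a limited sponsor group is unblinded for real-time safety review (Section 4.2.3; also Section 9.4). Section 6.8.3 does not say who must read the values, and Section 8 sends safety issues to the sponsor immediately to decide on continuation. Unscheduled laboratory samples are allowed at any time (Sections 8.2 and 8.2.4). Sponsor staff could therefore see three high values and direct discontinuation without breaching the blind. This stands. What is missing is any text that assigns this task for this rule or says what starts the extra sampling.

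Nor must a stop in this protocol be completed from scheduled samples. Creatine kinase has a stopping limit but is not in Table 6, and the kidney rule in Section 7.1.4 relies on a triggered repeat. Section 8.2.4 asks for clinically significant abnormal values to be repeated. This also stands, and it is why the window counts should not carry more weight. But the kidney rule states its trigger and the timing of the repeat; the hyperglycaemia rule does neither.

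The protocol's glucose terms are also loose. The entry limit at admission is called FPG, although the glucose measurement that Table 1 clearly specifies at admission is the fingerstick. Three readings over 3 days fits a once-daily fingerstick, so sites may well read the rule that way. That is plausible, but the lead-in to criterion 18 refers to the laboratory, and the uncertainty itself supports naming the measurement.

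Finally, the low-side text in Section 8.2.4.1 governs event recording, not a stop. It is a usable model for confirmation, not proof of an omission.

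**Conclusion.** Wrong as written, with minor impact. The rule names a measurement scheduled on at most 2 consecutive on-treatment mornings in Cohort 1, and on single mornings in a later cohort without the Day 28 profile. Its results do not go to the site. The rule can be met only by unscheduled samples reviewed by unblinded sponsor staff, or by treating the fingerstick as plasma glucose, and the protocol states neither route. The cross-reference from Section 7.1.3 to Section 8.2.4.2 is an error.

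The practical risk is modest. Participants are inpatients with a fingerstick that the site sees each morning, sites may share those readings with the sponsor, and fasting glucose above 270 mg/dL at screening or admission is excluded.

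The conclusion rests on reading fasting plasma glucose as a laboratory value and on counting the 24H sample as the next morning's fasting value. It does not depend on the Day 8 and Day 14 visits.

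**What to change.** In Sections 6.8.3 and 8.2.4.1, define the trigger as a fasting fingerstick above 270 mg/dL on 3 consecutive inpatient mornings. In Section 7.1.3, replace the reference to 8.2.4.2 with 8.2.4.1.

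To meet the confirmation requirement in Section 7.1.3, send one venous sample to the laboratory and have unblinded sponsor staff tell the investigator only whether the value is confirmed or not. State this as an exception to the withholding rule in Section 8 and Appendix 2. The 270 mg/dL threshold can stay.

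The cost is a clarification letter or short amendment: about one sentence in each of Sections 6.8.3 and 8.2.4.1, one corrected cross-reference, and the stated exception. No routine procedure is added, because the fingerstick is already taken daily. A participant who triggers the rule has one extra blood draw, and the relayed answer carries a small risk of hinting at treatment assignment.
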